| Grade 4 (> 10.0 x ULN)  | Permanently discontinue patient from LDK378   |
| AST or ALT   |   |
| Grade 1 (> ULN and ≤ 3.0 x ULN)   | Maintain dose level with LFTs*** monitored per protocol   |
| Grade 2 (> 3.0 and ≤ 5.0 x ULN) without total bilirubin elevation to > 2.0 x ULN  | Maintain dose level with LFTs*** monitored per protocol   |
| Grade 3 (> 5.0 and ≤ 20.0 x ULN) without total bilirubin elevation to > 2.0 x ULN   | Omit dose until resolved to ≤ Grade 1, then ↓ 1 dose level  |
| Grade 4 (> 20.0 x ULN) without total bilirubin elevation to > 2.0 x ULN   | Omit dose until resolved to ≤ Grade 1, then ↓ 1 dose level  |
| AST or ALT and concurrent Total bilirubin  |   |
| AST or ALT > 3.0 x ULN with total bilirubin > 2.0 x ULN in the absence of cholestasis or hemolysis  | Permanently discontinue patient from LDK378. Refer to Section 6.3.2.2 for additional follow-up.                                     |
| AST or ALT > 5.0 and ≤ 20.0 x ULN with total bilirubin > 1.5 and ≤ 3.0 x ULN  | Permanently discontinue patient from LDK378 if event reoccurs after dose reduction.   |
| PANCREATIC   |   |
| Amylase and/or lipase evaluations (in absence of clinical symptoms)   |   |
| Grade 1 (> ULN and ≤ 1.5 x ULN)   | Maintain dose level   |
| Grade 2 (> 1.5 - 2.0 x ULN)   | Maintain dose level   |
| Grade ≥ 3 (> 2.0 x ULN)   | Omit dose until resolved to ≤ Grade 1, then ↓ 1 dose level  |
| Note: Withhold LDK378 for acute onset of new or progressive unexplained abdominal symptoms, such as severe pain or vomiting; perform diagnostic procedures (e.g., abdominal CT scan or ultrasound) to exclude pancreatic pathology. |   |
| RENAL  |   |

| Worst toxicity (CTCAE 4.03 Grade)*               | Dose Modifications for LDK378  |
|---|---|
| Serum creatinine                                 |   |
| Grade 1 (>1 and ≤1.5 x baseline; >ULN and ≤ 1.5 x ULN)  | Maintain dose level   |
| Grade 2 (>1.5 and ≤3.0 x baseline; > 1.5 and ≤ 3 x ULN) | Omit dose until resolved to ≤ Grade 1, then:
If resolved in ≤ 7 days, then maintain dose level
If resolved in > 7 days, then ↓ 1 dose level                         |
| Grade 3 (>3.0 x baseline; > 3.0 and ≤ 6.0 x ULN)        | Omit dose until resolved to ≤ Grade 1, then ↓ 1 dose level  |
| Grade 4 (> 6.0 x ULN)                                   | Permanently discontinue patient from LDK378   |
| GASTROINTESTINAL                                 |   |

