- For patients with normal ALT and AST and TBIL value at baseline: AST or ALT > 3.0 x ULN combined with TBIL > 2.0 x ULN
- For patients with elevated AST or ALT or TBIL value at baseline: [AST or ALT > 2 x baseline AND > 3.0 x ULN] OR [AST or ALT > 8.0 x ULN], combined with [TBIL > 2 x baseline AND > 2.0 x ULN]

Medical review needs to ensure that liver test elevations are not caused by cholestasis, defined as: ALP elevation > 2.0 x ULN with R value (ALT/ALP in x ULN) < 2 in patients without bone metastasis, or elevation of ALP liver fraction in patients with bone metastasis.

Note: (The R value is calculated by dividing the ALT by the ALP, using multiples of the ULN for both values. It denotes the relative pattern of ALT and/or ALP elevation is due to cholestatic or hepatocellular liver injury).

In the absence of cholestasis, these patients should be immediately discontinued from study drug treatment, and repeat LFT testing as soon as possible, preferably within 48 hours from the awareness of the abnormal results. The evaluation should include laboratory tests, detailed history, physical assessment and the possibility of liver metastasis or new liver lesions, obstructions/compressions, etc:

- Laboratory tests should include ALT, AST, albumin, creatinine kinase, total bilirubin, direct and indirect bilirubin, GGT, prothrombin time (PT)/INR and alkaline phosphatase.
- A detailed history, including relevant information, such as review of ethanol, concomitant medications, herbal remedies, supplement consumption, history of any pre-existing liver conditions or risk factors, should be collected.
- Further testing for acute hepatitis A, B, C or E infection and liver imaging (eg, biliary tract) may be warranted.
- Additional testing for other hepatotropic viral infection (CMV, EBV or HSV), autoimmune hepatitis or liver biopsy may be considered as clinically indicated or after consultation with specialist/hepatologist.

All cases confirmed after repeat testing and meeting the laboratory criteria defined above, with no other alternative cause for LFT abnormalities identified should be considered as "medically significant", these cases will meet the definition of SAE ([Section 7.2.1](#)) and reported as SAE using the term "potential drug-induced liver injury". All events should be followed up with the outcome clearly documented.

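### Two rows of Table 6-4 give incompatible stopping instructions for AST/ALT >5.0 to ≤20.0 x ULN with bilirubin >2.0 to ≤3.0 x ULN when there is no cholestasis or hemolysis

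*Protocol*

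**What the plan says.** Protocol Section 6.3.1, Table 6-4, has a sub-heading for AST or ALT with concurrent total bilirubin. Two rows stand under it.

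- **First row.** Trigger: "AST or ALT > 3.0 x ULN with total bilirubin > 2.0 x ULN in the absence of cholestasis or hemolysis". Instruction: "Permanently discontinue patient from LDK378. Refer to" Section 6.3.2.2, for follow-up.
- **Second row.** Trigger: "AST or ALT > 5.0 and ≤ 20.0 x ULN with total bilirubin > 1.5 and ≤ 3.0 x ULN". Instruction: "Permanently discontinue patient from LDK378 if event reoccurs after dose reduction".

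Just above them, the row for raised transaminases alone is headed "Grade 3 (> 5.0 and ≤ 20.0 x ULN) without total bilirubin elevation to > 2.0 x ULN". It tells the site to withhold the drug until recovery and then go down one dose level.

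Section 6.3.2.2 defines potential drug-induced liver injury by baseline status. With normal baseline values it uses the first row's thresholds. The other criterion begins "For patients with elevated AST or ALT or TBIL value at baseline: [AST or ALT > 2 x baseline AND > 3.0 x ULN". It offers AST or ALT above 8.0 x ULN as an alternative, and adds bilirubin above both twice baseline and 2.0 x ULN. For patients who meet either criterion it says: "In the absence of cholestasis, these patients should be immediately discontinued from study drug treatment".

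**The concern.** A dose-modification table should give one instruction for each set of laboratory values. Here one set meets two rows of the same table. The first row ends treatment at the first event. The second makes permanent discontinuation conditional on recurrence after a reduction, which presupposes that the patient went on treatment again after the first event.

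Section 6.3.2.2 treats these combined elevations as possible drug-induced liver injury and as clinically important. Protocol Section 12 permits no authorized deviations, so a site that acts on one row could be recorded as departing from the other. SAP Section 2.3 tabulates failures to withdraw a patient as required. SAP Section 2.8.1 tabulates adverse events leading to discontinuation separately from those leading to dose adjustment or interruption. How such a case is classified would depend on which row the site took to govern. These are descriptive tables, so the main stake is patient management.

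**Working it through.** The plan states no figure to reproduce. The check sets the trigger regions side by side, in multiples of ULN.

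| | AST or ALT | Bilirubin | Cholestasis/hemolysis |
|---|---|---|---|
| First row | >3.0 | >2.0 | must be absent |
| Second row | >5.0 to ≤20.0 | >1.5 to ≤3.0 | no condition |
| Both rows | >5.0 to ≤20.0 | >2.0 to ≤3.0 | absent |

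**1. No cholestasis or hemolysis.** ALT 10 with bilirubin 2.5 meets the first row (10 > 3.0 and 2.5 > 2.0) and the second (5.0 < 10 ≤ 20.0 and 1.5 < 2.5 ≤ 3.0). ALT 10 with bilirubin 1.8 meets only the second. At bilirubin 2.5, ALT 4 meets only the first row, while ALT 15 also meets the second, whose stopping rule is conditional. The higher transaminase value thus brings in the less immediate instruction.

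**2. Cholestasis or hemolysis present.** The first row drops out, so there is no overlap. For bilirubin >2.0 to ≤3.0 the second row stands alone and states only what follows a recurrence. No other row fills the gap:
- the grade 3 AST/ALT row excludes bilirubin above 2.0;
- the grade 2 bilirubin row requires ALT or AST of at most 3.0.

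The general guidance in Section 6.3.1 covers only toxicities outside Table 6-4. Section 6.2.4 has a general hold-and-resume provision, but for dose-limiting toxicities, which are cycle 1 events.

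**3. Bilirubin >1.5 to ≤2.0.** Only the second row of the pair applies. The grade 3 AST/ALT row supplies a first action that is compatible with it. There is no conflict here.

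**4. Footnotes to Table 6-4.** The instruction to act on the worst preceding toxicity does not choose between two rows that describe the same values. The footnote on purely indirect bilirubin applies to grade 3 or 4, which the table puts above 3.0, outside the overlap. No footnote sets precedence.

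**5. Section 6.3.2.2.** Take baseline ALT 4 (exclusion criterion 3 allows up to 5 with liver involvement) and assume baseline bilirubin 1.0. Let ALT rise to 7 and bilirubin to 2.5, without cholestasis or hemolysis.
- First row: met (7 > 3.0; 2.5 > 2.0).
- Second row: met (5.0 < 7 ≤ 20.0; 1.5 < 2.5 ≤ 3.0).
- Section 6.3.2.2: transaminase part not met, since 7 is not above 2 × 4 = 8 and not above 8.0.

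Neither row carries a baseline-relative threshold. In addition, the section's exemption names cholestasis only, whereas the first row's names cholestasis or hemolysis.

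**6. Size.** Protocol Section 2.6 reports concurrent ALT >3 x ULN and bilirubin >2 x ULN with normal alkaline phosphatase in less than 1% of patients in clinical studies. Amendment 8 reports twelve patients still on treatment. If that rate carried over to them, the expected number would be below 12 × 0.01 = 0.12.

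**The case against.** The best defence is structural. The grade 2, 3 and 4 rows for raised AST or ALT all exclude bilirubin above 2.0 x ULN. This suggests that non-cholestatic cases above 2.0 belong to the first row, leaving the second for bilirubin >1.5 to ≤2.0 or for cholestatic or hemolytic cases. That reading is coherent, but the table nowhere says it. The second row's bilirubin range runs to 3.0 and it carries no cholestasis or hemolysis condition.

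A second argument is that the rows are not opposite commands. This stands. The second row does not order a site to reduce and continue at the first event; continuation is only implied. A reader might infer that the protocol expressly instructs continuation against a stop rule, but the wording does not go that far. The rows are incompatible in when they require permanent discontinuation.

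A third is that the event is rare, recruitment was complete, and all patients had completed at least 6 cycles according to the Amendment 8 rationale. This also stands. It limits the expected number of affected patients but does not remove the ambiguity.

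**Conclusion.** The inconsistency is real and follows from current protocol text alone. It is confined to AST or ALT >5.0 to ≤20.0 x ULN with bilirubin >2.0 to ≤3.0 x ULN and no cholestasis or hemolysis. In the same range with cholestasis or hemolysis, the defect is instead a missing first-event action in the table.

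Three stronger readings are not supported:
- **That the second row never has a first-event action.** The grade 3 AST/ALT row gives one up to bilirubin 2.0, and the first row gives one above 2.0 without cholestasis or hemolysis.
- **That Section 6.3.2.2 requires permanent discontinuation throughout the overlap.** It calls for immediate discontinuation, does not use the word permanent, and has different thresholds for patients with elevated baseline values.
- **That the problem is frequent because 26.7% of adults at 750 mg had grade 3-4 ALT (Table 1-1).** That figure ignores bilirubin; the less than 1% figure is closer.

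Even that closer figure is only a guide. It comes from other clinical studies, uses a lower ALT threshold with no upper limit on ALT or bilirubin, and requires normal alkaline phosphatase. Carrying it over to these patients is an assumption. The point rests on the seriousness of the liver pattern and the ambiguity for patients on treatment, not on frequency. No planned analysis method is affected.

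**What to change.** The two Table 6-4 rows and Section 6.3.2.2 must be reconciled so that every combination of transaminase level, bilirubin level, cholestasis or hemolysis status, and baseline status leads to exactly one instruction, including at first occurrence. If one row is meant to override another, the table should say so. Which rule is right is a clinical decision for the sponsor and investigators, and none is proposed here.

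The cost is a wording change to the table and one section, made through a protocol amendment as Section 12.1 requires, and a communication to sites. Sample size, data collection and the SAP's methods need not change.

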### 6.3.2 Follow-up for toxicities

An unscheduled visit should be performed in all cases below where toxicity monitoring is recommended more frequently than defined by the schedule of assessments in (Table 7-1). For details and frequency refer to Table 6-5.

#### 6.3.2.1 Guidelines for the follow-up of laboratory hematologic abnormalities

In case of any occurrence of febrile neutropenia, neutropenia  $\geq$  grade 3, anemia grade 4, or thrombocytopenia  $\geq$  grade 3, white blood cell count with differential (including neutrophil count), platelet count and hemoglobin must be measured after 3 days and then at least once a week (or more frequently if clinically indicated) until the event resolves to  $\leq$  grade 2 or baseline. Subsequent monitoring must be performed every 3 weeks (21 days).

Hematopoietic growth factors (e.g., erythropoietins, G-CSF, and GM-CSF) are not to be administered prophylactically. Use of these drugs should be reserved to patients with severe neutropenia and anemia as per the labeling of these agents.

#### 6.3.2.2 Guidelines for the follow-up of liver laboratory abnormalities

In patients with any clinically relevant liver laboratory abnormality, as defined below, hepatic toxicity monitoring must include **ALL** of the following LFTs: albumin, ALT, AST, total bilirubin (fractionated if total bilirubin  $>$  1.5x ULN, and any additional evaluation suggested by these results should be performed as clinically indicated), ALP. Note: for patients with Gilbert Syndrome, total and direct bilirubin must be monitored, but intensified monitoring applies to changes in direct bilirubin only.

In case of any occurrence of ALT/AST/total bilirubin increase to grade 2, the LFTs must be monitored weekly (or more frequently if clinically indicated) until the event resolves to  $\leq$  grade 1. Thereafter monitoring must be continued every 2 weeks (or more frequently if clinically indicated) for two additional cycles (e.g. 6 weeks). If there is no recurrence of  $\geq$  grade 2 ALT/AST/total bilirubin elevations during this period, subsequent monitoring must be performed every 3 weeks. For patients with liver metastasis and grade 2 AST/ALT at baseline, increased monitoring is required for grade 3/4 AST/ALT; follow guidelines for grade 3 or 4 AST/ALT.

In case of any occurrence of ALT/AST/total bilirubin increase to grade 3 or 4, LFTs must be monitored weekly (or more frequently if clinically indicated) until the event resolves to  $\leq$  grade 1. Thereafter monitoring must be continued every 2 weeks (or more frequently if clinically indicated) for four additional cycles (e.g., 12 weeks). If there is no recurrence of  $\geq$  grade 2 ALT/AST/total bilirubin elevations during this period, subsequent monitoring must be performed every 3 weeks.

Patients who discontinue study treatment due to liver toxicity must be monitored weekly (or more frequently if clinically indicated) until the event resolves to  $\leq$  grade 1 or stabilization occurs (no CTCAE grade change over 3 weeks). Refer to Table 6-5.

Patients with transaminase increase combined with total bilirubin (TBIL) increase may be indicative of potential DILI, and should be considered as clinically important events.

The threshold for potential DILI may depend on the patient's baseline AST/ALT and TBIL value; patients meeting any of the following criteria will require further follow-up as outlined below:

- For patients with normal ALT and AST and TBIL value at baseline: AST or ALT > 3.0 x ULN combined with TBIL > 2.0 x ULN
- For patients with elevated AST or ALT or TBIL value at baseline: [AST or ALT > 2 x baseline AND > 3.0 x ULN] OR [AST or ALT > 8.0 x ULN], combined with [TBIL > 2 x baseline AND > 2.0 x ULN]

Medical review needs to ensure that liver test elevations are not caused by cholestasis, defined as: ALP elevation > 2.0 x ULN with R value (ALT/ALP in x ULN) < 2 in patients without bone metastasis, or elevation of ALP liver fraction in patients with bone metastasis.

Note: (The R value is calculated by dividing the ALT by the ALP, using multiples of the ULN for both values. It denotes the relative pattern of ALT and/or ALP elevation is due to cholestatic or hepatocellular liver injury).

In the absence of cholestasis, these patients should be immediately discontinued from study drug treatment, and repeat LFT testing as soon as possible, preferably within 48 hours from the awareness of the abnormal results. The evaluation should include laboratory tests, detailed history, physical assessment and the possibility of liver metastasis or new liver lesions, obstructions/compressions, etc:

- Laboratory tests should include ALT, AST, albumin, creatinine kinase, total bilirubin, direct and indirect bilirubin, GGT, prothrombin time (PT)/INR and alkaline phosphatase.
- A detailed history, including relevant information, such as review of ethanol, concomitant medications, herbal remedies, supplement consumption, history of any pre-existing liver conditions or risk factors, should be collected.
- Further testing for acute hepatitis A, B, C or E infection and liver imaging (eg, biliary tract) may be warranted.
- Additional testing for other hepatotropic viral infection (CMV, EBV or HSV), autoimmune hepatitis or liver biopsy may be considered as clinically indicated or after consultation with specialist/hepatologist.

All cases confirmed after repeat testing and meeting the laboratory criteria defined above, with no other alternative cause for LFT abnormalities identified should be considered as "medically significant", these cases will meet the definition of SAE ([Section 7.2.1](#)) and reported as SAE using the term "potential drug-induced liver injury". All events should be followed up with the outcome clearly documented.

### 6.3.2.3 Guidelines for the follow-up of renal laboratory abnormalities

In case of any occurrence of serum creatinine grade 2, tests must be performed weekly (or more frequently if clinically indicated) until the event resolves to  $\leq$  grade 1. Subsequent monitoring must be performed every 3 weeks.

In case of any occurrence of serum creatinine  $\geq$  grade 3, tests must be performed twice weekly (or more frequently if clinically indicated) until the event resolves to  $\leq$  grade 1. Subsequent monitoring must be performed every 3 weeks.

#### **6.3.2.4 Guidelines for monitoring pneumonitis**

Monitor patients for pulmonary symptoms indicative of pneumonitis. In addition, withhold LDK378 for acute onset of new or progressive unexplained pulmonary symptoms, such as dyspnea, cough and fever and during diagnostic workup for pneumonitis/ILD. Exclude other causes of pneumonitis, and follow dose modification guidelines as described in [Table 6-4](#).

#### **6.3.2.5 Guidelines for the treatment of study treatment-induced diarrhea**

The investigator should consider/investigate potential concomitant medication-, food-, or comorbidity-driven causes of diarrhea (including infectious causes) and remedy these causes if possible (e.g., discontinuation of concomitant medication, dietary modification, treatment of comorbidity).

**The patient should be actively monitored for signs of dehydration and instructed to take preventive measures against dehydration as soon as diarrhea occurs.**

Antidiarrheal medication must be initiated at the first sign of abdominal cramping, loose stools or overt diarrhea. Concomitant medication for the treatment of diarrhea should follow local practices and the Investigator's best judgment and may follow "the recommended guidelines for the treatment of cancer treatment-induced diarrhea" ([Benson et al 2004](#)). For example:

- For uncomplicated diarrhea (grade 1 or 2 without complicating signs or symptoms), loperamide given at the usual pediatric dose as per local Label, along with oral hydration, and dietetic measures should be considered. Note: complicating signs or symptoms include: moderate to severe cramping, decreased performance status, fever, neutropenia, frank bleeding or dehydration.
- For complicated diarrhea (all grade 3 or 4, grade 1-2 with complicating signs or symptoms), management should involve IV fluids, and consider treatment with antibiotics (e.g., fluoroquinolone) should be given.

Dose adaptation of LDK378 in case of treatment-related diarrhea must follow the guidelines presented above in [Table 6-4](#).

#### **6.3.2.6 Guidelines for the treatment of study treatment-induced nausea and vomiting**

Nausea and vomiting are among the most frequently reported AEs following treatment with LDK378 and patients must therefore be closely monitored for the appearance of these AEs.

The investigator should also consider/investigate potential concomitant medication-, food-, or comorbidity-driven causes of nausea and/or vomiting and remedy these causes if possible (e.g., discontinuation of concomitant medication, dietary modification, treatment of comorbidity).

Individualized supportive and anti-emetic treatment should be initiated, as appropriate, at the first signs and/or symptoms of these AEs. In patients with vomiting, the patient should be monitored for signs of dehydration and instructed to take preventive measures against dehydration.

Concomitant medication for the treatment of nausea and/or vomiting should follow local practices and the Investigator's best judgment. For moderately emetogenic drugs, such as LDK378, International Guidelines for anti-emetic treatment recommend early treatment with 5-HT3-receptor antagonists (5-HT3RAs).

Dose adaptation of LDK378 in case of treatment related nausea and/or vomiting must follow the guidelines presented above in [Table 6-4](#).

### **6.3.2.7 Guidelines for the treatment of hypophosphatemia**

In the phase I study [[CLDK378X2101](#)] conducted in adult patients, as of 31-Oct-2013, there were 9 cases of grade 3 hypophosphatemia observed in all dose groups, one of which was a DLT that contributed to the MTD determination – this patient was able to continue LDK378 at the same dose. One patient in the 750 mg group had a grade 3 hypophosphatemia that resolved after dose adjustment or interruption; in the remaining 8 cases, patients were able to continue therapy without dose modification. Hypophosphatemia was not among the commonly reported AE (6.3%), regardless of relationship to LDK378 treatment.

Therefore, phosphate levels will be checked during treatment. For any grade of hypophosphatemia during the study, treatment with phosphate supplements should be given as clinically indicated, and the LDK378 dose can be maintained.

### **6.3.2.8 Guidelines for the follow-up of laboratory pancreatic abnormalities**

In case of any occurrence of lipase or amylase increase to grade 3 or 4, both lipase and amylase must be monitored weekly (or more frequently if clinically indicated) until the event resolves to  $\leq$  grade 1 (or to baseline).

After resumption of dosing, monitoring must be continued weekly (or more frequently if clinically indicated) for one additional cycle (i.e. 3 weeks). If there is no recurrence of  $\geq$  grade 2 amylase or lipase elevations during this period, subsequent monitoring must be performed every 3 weeks.

Patients who discontinue study treatment due to pancreatic toxicity must be monitored weekly (or more frequently if clinically indicated) until the event resolves to  $\leq$  grade 1 or stabilization occurs (no CTCAE grade change over 3 weeks). Refer to [Table 6-5](#).

If amylase and/or lipase elevations are accompanied by new or progressive unexplained abdominal symptoms such as severe pain or vomiting, withhold ceritinib, then perform diagnostic procedures (e.g., abdominal CT scan or ultrasound) to exclude pancreatic pathology.

See also dose modification guidelines described in [Table 6-4](#).

